## Study History

Submission Type	Initial	Review Type	Expedited	Decision	Approved
-----------------	---------	-------------	-----------	----------	----------

# Initial Submission

---

## Getting Started

*Initial Submission Application, V9, 1 Mar 2021*

---

### About Cayuse IRB

Cayuse IRB is an interactive web application. As you answer questions, new sections relevant to the type of research being conducted may appear. You do not have to finish the application in one sitting. All information can be saved.

For more information about the IRB submission Process, IRB Tracking, and Cayuse IRB Tasks, please refer to the [Cayuse IRB Support website](#) or by clicking the orange question mark at the bottom right hand corner.

---

### Getting Started

Throughout the submission, you may be required to provide the following information:

- Detailed Study Information
- Study Recruitment
- Data Storage Information
- Details on Reimbursement
- Details if a waiver of Informed Consent is requested

---

### Other Important Information

- You cannot begin your study until a **formal approval letter** from the chair of the IRB has been received.

- The IRB meets as needed during the regular academic year. Please submit the application as soon as possible.

---

## **Guidelines**

- Please go to the [NUS-IRB website](#) to download the relevant guidelines.
- Please note that guidelines are accessible to NUS researchers only.
- For non-NUS researchers, please contact [[contact]](mailto:[contact]).

---

\*required

## **Confirmation**

---

I have read the information above and I am ready to begin my submission.

### **Simplified Title**

---

*For use in recruitment documents, e.g. Participant Information Sheet & Consent Form, advertisements.*

**Please leave blank if main protocol title will be used in study documents.**

ReCognition Study

### **Second Simplified Title**

---

*Is there a second Simplified Title for this project?*

No

Yes

---

### **Key Personnel**

---

*Please list the key personnel on this project.*

### **Principal Investigator's Alternate Email Address**

---

### **Student Principal Investigator**

---

*Is the PI a student at NUS?*

---

No

Yes

---

### **Primary Contact's Alternate Email Address**

---

### **Co-Investigator(s)'s Alternate Email Address(es)**

---

### **External Co-Investigator(s)**

---

*If applicable.*

***Please do not include collaborators if they are not co-investigators in this study.***

#### **Will there be external co-investigators on this study?**

---

No

Yes

\*required

### **Funding**

---

#### **Is this project funded?**

No

Yes

### **Sponsor(s)**

---

*Please find the sponsor(s) in the sponsor finder below.*

**Name**

-

- [Name - A to Z](#)
- [Name - Z to A](#)

NATIONAL HERITAGE BOARD  
(No SAP BizPart#) LIEN FOUNDATION

*If your project sponsor(s) cannot be found in the sponsor finder above, please list them down below:*

---

---

\*required

**Status of Award**

Approved

In-Progress

\*required

**Award Amount**

*Please provide the award amount in Singapore dollars (SGD). Please add a "\$" to the amount awarded (e.g., \$1000).*

376114

**Benefits**

*The financial benefits or other benefits derived from this study to the PI/Co-I(s)/Department/Institution are as follows (if any):*

\*required

**Indirect Research Costs (IRC)**

*If this research is sponsored by a commercial company, and the company has an interest on the results arising from this research, please advise if NUS has already charged 20% indirect costs / fees for this research. If not, please note that a review fee of SGD\$500 will be applicable (SGD\$535 inclusive of 7% GST).*

✓ N/A

Yes, IRC charged

No, IRC not charged

\*required

### **External IRB(s)**

---

*Has the protocol for this project been submitted to or approved by other local/overseas IRBs?*

✓ No

Yes

**Social, behavioral, and education research (SBER)** encompasses a range of methodologies and tackles questions that seek to improve our understanding of human behavior, attitudes, beliefs, and interactions as well as social and economic systems, organizations, and institutions.

**Human Tissue Framework:** Please refer [here](#) for more information and the [HTF Self-Checklist](#) for PI.

**Human Biomedical Research:** Please refer to the link to the [Act](#) for the definition and the [HBR Self-Checklist](#) for PI.

---

## Review Classification

---

\*required

### Social, Behavioral, Educational Research (SBER) Category

---

*Does this project fall under the Social, Behavioral, Educational Research (SBER) category?*

Yes

No

\*required

### e-Declaration

---

*Is the PI submitting an [e-Declaration](#)?*

Yes

No

\*required

## **Human Biomedical Research Act (HBRA)**

---

*Is your study regulated under the Human Biomedical Research Act (HBRA)?*

Yes

No

## **Study Classification: Human Biomedical Research and Human Tissue Framework**

---

\*required

*This research is intended to study:*

1.a

**The prevention, prognostication, diagnosis or alleviation of any disease, disorder or injury affecting the human body**

No

Yes

\*required

*Please briefly elaborate.*

1.a

This mixed-methods study evaluates the impact of "Refresh and Reconnect!" (R&R!), a museum-based heritage programme, launched by the National Museum of Singapore, on the health and well-being of persons with cognitive impairment (PWCIs).

The study seeks to gain insights into the factors, contexts, and mechanisms that influence the effect and implementation of the museum-based intervention, as well as to understand how participation in the programme affects participants' understanding and perception of the museum as a potential place to enhance one's health and well-being so as to provide insights leading to the development of effective, non-pharmacological interventions for PWCIs.

---

\*required

*This research is intended to study:*

1.b

**The restoration, maintenance or promotion of the aesthetic appearance of human individuals through clinical procedures or techniques**

No

Yes

\*required

*This research is intended to study:*

1.c

**The performance or endurance of human individuals**

No

Yes

\*required

*This research involves:*

2.a

**Subjecting an individual to any intervention (including any wilful act or omission) that has a physical, mental or physiological effect (whether temporary or permanent) on the body of the individual**

No

Yes

\*required

*Please briefly elaborate.*

---

This study would recruit participants with mild cognitive impairments or mild dementia, and invite them to participate in an interactive 6-week programme in National Museum of Singapore. This programme would include some physical requirement of the participants to walk around the museum, do art and craft, cooking, and interact with other participants and

artists.

2.a

For programme evaluation, participants are subject to several non-invasive screenings and questionnaires which include the following: cognitive impairment screening, quality of life, loneliness, anxiety and depression, and motivations to learn. These questionnaires will be administered 2 times: up to 1 month before the program, and approximately 1 to 2 weeks after the program. These questionnaires may require participants to evaluate their own mental well-being and social relationships during the assessment period. Several participants will also be selected for in-depth interviews which will explore their responses in surveys further, in addition to understanding more deeply about participants' experiences with the programme or the museum space.

---

\*required

*This research involves:*

2.b

**The use of any human biological material**

No

Yes

\*required

*This research involves:*

2.c

**The use of any individually-identifiable health information**

No

Yes

\*required

*This research involves:*

2.d

**The use of human gametes or human embryos**

No

Yes

\*required

*This research involves:*

2.e \_\_\_\_\_

**The use of cytoplasmic hybrid embryos**

No

Yes

\*required

*This research involves:*

2.f \_\_\_\_\_

**The introduction of any human-animal combination embryo into an animal or a human**

No

Yes

\*required

*This research involves:*

2.g \_\_\_\_\_

**The introduction of human stem cells (including induced pluripotent stem cells) or human neural cells into an animal at any stage of development (including a prenatal animal fetus or animal embryo)**

No

Yes

\*required

*This research involves:*

2.h \_\_\_\_\_

**Any entity to be created as a result of any process referred to in 2.f or 2.g**

Yes

No

\*required

**Will the research fall within the Second Schedule of the Human Biomedical Research Act?  
[Biomedical Research (HBRA) Studies only]**

---

No

Yes

\*\*\*\*\*  
\*\*\*\*\*

---

**NUS-IRB OFFICE ONLY [Biomedical Research (HBRA) Studies only]**

1.a Yes

---

1.b No

---

1.c No

---

2.a No

---

2.a Yes

---

2.b No

---

2.c No

---

2.d No

---

2.e No

---

2.f No

---

2.g No

---

2.h No

---

\*required

## Abstract

---

*Please provide an abstract of this study in no more than 300 words.*

*The abstract must be self-contained so that it can serve as a succinct and accurate description of the application when separated from it.*

### Background

Dementia and mild cognitive impairment are a rising concern for the ageing population in Singapore, leading to diminished quality of life and health outcomes. Arts-based interventions in a museum setting have been shown to improve cognitive health and well-being for Persons with Cognitive Impairment (PWCIs), however little is known about the relationship of heritage-based interventions on the health and well-being of PWCIs.

### Methods

This mixed-methods study evaluates the 6-week "Refresh and Reconnect!" programme (R&R!), a museum-based heritage programme including guided artist-led activities and tours of the National Museum of Singapore.

- i) In the quantitative study (n = 64-120 PWCIs), assessments will be conducted at 2 time points (pre-programme, post-programme) to evaluate cognitive, social, and mental well-being.
- ii) In the qualitative study, ethnographic observations of the R&R! programme; ethnographic interviews with staff (n= max 3), & artists (n= max 6); and in-depth interviews with PWCIs (n=16) will be used to elicit the underlying context-mechanisms-outcomes which enable R&R! success. Programme volunteers will also be engaged through casual or informal conversations as part of the ethnographic observations.

### Expected outcomes

The study aims to provide valuable insights into the development of effective, non-pharmacological interventions for PWCIs. These findings are of significant public health importance for Singapore, potentially informing policy decisions, resource allocation, and healthcare strategies to better support PWCIs, ultimately improving their quality of life. Findings of the study may also contribute to similar heritage-based programmes in future, contributing to the understanding of key elements of programme success, and for whom these programmes are effective for.

\*required

## Specific Aims

---

The study will explore and assess the impact of "Refresh and Reconnect!", a 6-week heritage-based intervention programme organised by the National Museum of Singapore (NMS), which includes guided

gallery tours led by the museum's Care Facilitator volunteers and artist-led hands-on activities based on various art forms.

The overall objectives of the study are to understand the following:

1. To what extent, and how does participation in the "Refresh and Reconnect!" programme impact health and well-being of PWClIs?
2. To what extent, and how does participation in the programme affect the study participants' understanding and perception of the museum as a potential place to enhance one's health and well-being? *[Note: Study Participants include all who are participating in the study such as PWClIs and those who are implementing (e.g. museum staff), facilitating (e.g. artists) and assisting (e.g. volunteers) with the R&R! Programme]*
3. What are the contexts and mechanisms that influence the implementation of the programme?

## **Hypothesis**

---

\*required

## **Preliminary Studies**

---

*State those studies relevant to this project.*

**Quantitative:** The study team has previous experience conducting longitudinal surveys with older persons in the community (NUS-IRB: LS-18-387C)

**Mixed-methods:** The study team has also previously completed a study which involved the study team working with persons with dementia and their caregivers in a community setting to better understand caregiving needs (NUS-IRB: H-17-013)

**Qualitative:** The study team is also conducting a study which includes similar methodology to the qualitative component (NUS-IRB-2023-898), incorporating both in-depth interviews and ethnographic observations with service users.

\*required

**Human Subjects [Biomedical Research (HBRA) Studies]**

---

*Will this project involve the recruitment of human subjects?*

Yes

No

\*required

**Type of Study [Biomedical Research (HBRA) Studies]**

---

Human Biological Materials (excluding Human Tissues)

Human Tissue

Tissue Bank

**Restricted Research**

✓ Questionnaire / Survey / Interview / Focus Group Discussion

**Copy of questionnaire / survey / interview guide / focus group discussion guide**

---

*Please submit a copy of questionnaire / survey / interview guide / focus group discussion guide, if available.*

[ReCognition Baseline-Survey PWCI V1.docx](#)

[ReCognition MoCA Instructions \(English Singapore\).pdf](#)

[ReCognition Post-Survey PWCI V1.docx](#)

[ReCognition IDI Guide PWCI V1.docx](#)

[ReCognition Ethno Checklist V1.docx](#)

[ReCognition Programme Assessment PWCI V1.docx](#)

✓ Interventions / Invasive procedures

Use of Device(s)

Testing of Device(s)

Animal procedures

Other(s)

\*required

## **Procedures**

---

[figure not shown]
*Describe research procedures, including research visits (frequency and duration of procedure involved).*

A draft of the project agreement is attached for initial reference and review. The final terms of the project are in the process of finalisation. The study team will attach a signed version of the project agreement where available.

### **Study design**

The study will explore and assess the impact of “Refresh and Reconnect!”, on the health and well-being of persons with Mild Cognitive Impairment (MCI) or mild dementia - from here such individuals are referred to person(s) with cognitive impairment (PWCIs). “Refresh and Reconnect!” is a 6-week heritage-based intervention programme organised by the National Museum of Singapore (NMS), which includes guided gallery tours led by the museum’s Care Facilitator volunteers and artist-led hands-on activities based on various art forms.

The exploratory study adopts a quasi-experimental and mixed-methods design, incorporating *i) a quantitative component, and ii) a qualitative component*. The duration of each run of the “Refresh and Reconnect!” (R&R) programme is 6 weeks, and the data collection will take place over 4 programme rounds (Rounds 1 to 4), with 2 concurrent programme runs in each round, contributing to a total of 8 programme runs. For the period of study, participants enrolled into the R&R! programme will also be enrolled into the research study, with due informed consent. The study design for the first 2 rounds of the programme presented as below, and are repeated once more for a total of 8 programme runs:

## R&R! Programme Design

The programme will be delivered at the NMS by certified facilitators including trained art and music artists, and the museum's Care Facilitator volunteers. Each 6-week long run of the programme will be held over consecutive weeks, with each week having a single session of approximately 2 hours in duration. The sessions of the two concurrent runs of the programme in any given week will be held on different days of the week. Each PWCI involved will attend 6 sessions in total. A sample layout of the programme is given below.

### **WeekFocus area(s) (Runs 1 through 4)**

- 1 Introduction to Reunion and welcome session (the space, and museum)
- 2-3 Guided tour & Artist-led art workshop
- 4-5 Guided tour & Artist-led dance workshop
- 6 Celebration & programme conclusion

### **Focus area(s) (Runs 5 through 8)**

Guided tour & Artist-led drama workshop

## Programme Recruitment & Quantitative Sampling

NMS and the research team will conduct outreach with community partners to recruit suitable participants from day centres and Active Ageing Centres that support older persons living with cognitive impairment. Service providers will be approached based on their (i) willingness and interest to participate in the programme and by extension, the study as well as (ii) ability to recruit potential participants with mild cognitive impairment into the programme. Partners include the following organisations for the first 6 runs of the programme: NTUC Health (Senior Day Care @ Wisma Geylang Serai & Bukit Merah View), Dementia Singapore, Fei Yue (AAC & CREST-PDS programme @ Fajar Road), Sparkle Care @ Braddell Heights, Caregiving Welfare Association. NMS is continuing to seek out community partners for the 7th and 8th run of the programme at the time of this IRB application; the study team will amend the ethics application accordingly when these partners are confirmed. All interested and eligible participants for the programme will need to consent to the research study to participate in the R&R! programme.

Staff at the respective recruitment sites will refer interested participants to NMS and the research team for follow-up. Staff at the recruitment sites will seek their verbal consent to provide contact details to a member of the study team for them to explain the research and coordinate the **cognitive screener** and subsequent programme/research activities.

A member of the study team will subsequently contact the prospective participant(s) to explain the study further and administer the Montreal Cognitive Assessment (MoCA) screener - screening of participants may take place at a place of their choice (e.g. Home, void deck, etc.) or at the centre (e.g. Active Ageing Centre Dementia Daycare centre, etc.) from which they had been recruited. MoCA has been utilised in previous research to establish the mental capacity of PWCIs in independently consenting to research studies, medical decisions, and for surgery. Research studies (Karlawish et al., 2013; Vertennikoff, Walker, Biggs, & Robins 2017; Yang et al., 2024; Zietlow et al., 2020) have suggested a score of 22 out of 30 as the mental capacity threshold for informed consent. Participants whose MoCA scores are below 22 (out of 30) will not be eligible for this study.

Only PWCIs who meet the eligibility criteria will be enrolled into the study during the programme run. PWCIs who did not meet the eligibility criteria may still participate in the programme in a subsequent run (outside of the study period) subject to the discretion of NMS staff, but they will not be able to participate in the research entirely - NMS may consider this group of interested participants for other programmes within the museum well, with their consent. As not all participants screened with the MoCA will be eligible or willing to take part in the study, the study team will continue to screen participants until the required number of participants is met. Participants will undertake the informed consent process only after their eligibility has been ascertained with the screener; members of the research team will briefly explain prospective participants' involvement in the quantitative and qualitative components of the study. The study team will also highlight that participants may or may not be selected for in-depth interviews as not all PWCIs-participants will be recruited for this study procedure. The screening and subsequent informed consent process is to be conducted in-person and is expected to take no more than 20 minutes per participant in total (5-10 minutes for either screener or informed consent).

A maximum number of 15 participants will be recruited per programme run to account for attrition (minimum participation is n=8 per run). As two concurrent runs will take place at one time, a total of 16-30 participants will be recruited for study at each pre-programme time point. Transportation will be provided by NMS through a transport contractor, with costs borne by NMS or their relevant funding channels, independent of the research funding. Staff at NMS will liaise with staff from the relevant community partner organisations to organise and facilitate the transport of PWCIs for the R&R! programme. To facilitate ease of transporting PWCIs from participating centres, only PWCIs from the same centre will be enrolled in each run. Ideally, each run will consist of two participating centres (if possible). Participants will get their turn to participate in the programme depending on their centre's scheduled run.

### **Component (i): Quantitative Study**

A quasi-experimental, pre-post study design will be adopted, by comparing the baseline assessment and the post-program assessments of **all PWCIs-participants of each program run** (n=64-120). All PWCIs-participants recruited in the study will be surveyed at two time points (i) and (ii).

(i) The **pre-programme baseline assessment** will be conducted starting from one month leading up to the start of the program in each run for all PWCIs of those 2 concurrent runs. All study procedures may only begin after participants have been confirmed eligible and have undergone the informed consent process. Baseline

surveys will be conducted with this group of participants either at the site from which they had been recruited and may be conducted immediately following the informed consent process. Otherwise, participants may also request for baseline assessments to take place at a time and place of their convenience. Upon completion of the pre-programme baseline assessments, participants will receive the programme as usual (enrolment based on availability and logistics of NMS and participating centres)

(ii) The **post-programme assessment** will be administered to PWCI-participants approximately one to two weeks after the completion of the 6-week R&R! programme. Post-programme assessments, conducted by trained research staff, may similarly be done at the respective recruitment site of the PWCI-participant, or at a place of their convenience (e.g. home/place of residence, community open space). PWCI-participants will also be required to complete a brief museum-related assessment at the end of each session throughout the programme run.

All participants recruited for the study will be expected to **complete both quantitative surveys**. Interviewers will administer the study questionnaires in the participants' preferred language (English, Mandarin, Malay, or other dialects). The questionnaire will be administered in Qualtrics where possible. Each in-person survey is expected to **last no more than 1 hour** and will take place at a time and place of the participant's convenience. PWCI-participants may be accompanied by a CG during the interview if they require assistance, however no proxy will respond on the PWCI-participant's behalf. If participants are unable to complete the survey in a single session, they may request for the survey to be done over multiple sessions (with no charge to remuneration).

The pre-programme baseline assessment questionnaires will collect the following information for all PWCI-participants: socio-demographic, number of chronic diseases, stage of dementia (if applicable), status of activities of daily living (ADLs) and instrumental ADLs (IADLs), living arrangement. Both the pre-programme baseline assessment, as well as the post-programme assessment measure the following constructs:

- *Cognitive performance* (during screener; MoCA),
- *Health-related Quality of Life* (EQ-5D),
- *Quality of Life* (Control, Autonomy, Self-Realization, and Pleasure-11-SG; CASP-11-SG),
- *Anxiety & Depression* (Hospital Anxiety and Depression Scale; HADS),
- *Loneliness* (UCLA-LS-9 Loneliness scale),
- *Motivations to Learn* (Readiness-to-learn scale from Programme for the International Assessment of Adult Competencies (PIAAC))

In addition to the constructs measured above, PWCI will also be asked several open-ended questions relating to their experience of the programme, motivations to join the programme, as well as their previous experience with heritage-based or arts-based programmes. Responses from these questions, and engagement during the ethnographic observation will be used for selection of participants for the qualitative component and will also be analysed together with survey and in-depth interview responses; participants' responses from each research component will only be linked via the assigned unique participant ID.

After each session of the 6-week programme, participants will also answer a brief questionnaire [Labelled: "*ReCognition Programme Assessment PWCI*"] measuring their *Museum-based subjective well-being* (UCL Museum Wellbeing Measures toolkit). This measure will be administered in hard-copy paper, with each participant filling in one copy of the questionnaire at the end of the session (distributed either by NMS staff members of the research team). Each participant will either write their initials or first name on the

questionnaire for identification purposes - a member of the research team would subsequently key in these scores, pegged to respective participants' unique ID number. Subsequently once the scores are digitised and verified by another member of the research team, the hardcopy measurements will be shredded. This measure is expected to take **no more than 5 minutes** for participants to complete. Throughout the course of the study, participants would thus complete 6 instances of this questionnaire.

All health and well-being constructs at pre-programme baseline assessment and post-programme assessments will be compared using linear mixed models for repeated measurements. Analyses will be adjusted for potential socio-demographic or other confounders, collected at baseline. All data will be collected on Qualtrics and analysed on Stata 16, or similar statistical software packages.

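### The MoCA score that decides admission is also the pre value of the uncontrolled pre-post comparison, so the raw MoCA change can carry a regression-to-the-mean component of unknown sign; separately, the MoCA bounds contradict each other

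*Protocol*

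**What the plan says.** **Pre value.** Component (i): Quantitative Study lists cognitive performance among the constructs measured before and after the programme and marks it "during screener; MoCA". The elaboration of item 2.a in the study classification counts cognitive screening among the instruments and states: "These questionnaires will be administered 2 times: up to 1 month before the program, and approximately 1 to 2 weeks after the program". No second pre-programme MoCA appears.

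**Selection.** The screener comes before consent ("Participants will undertake the informed consent process only after their eligibility has been ascertained with the screener"), and "the study team will continue to screen participants until the required number of participants is met".

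**Bounds.** The sections differ:

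| Section | 10 or more years of education | Under 10 years |
|---|---|---|
| Inclusion Criteria; Exclusion Criteria | 22 to 27 | 22 to 26 |
| How will the mental capacity of elderly be screened?; Consent Process | above 22 and below 27, i.e. 23 to 26 | above 22 and below 26, i.e. 23 to 25 |

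Programme Recruitment & Quantitative Sampling gives only a lower limit: "Participants whose MoCA scores are below 22 (out of 30) will not be eligible for this study".

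**Analysis.** Component (i) compares baseline with post-programme assessments in all participants, with no control group. It uses linear mixed models adjusted for socio-demographic or other baseline confounders.

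**The concern.** A pre score restricted to between three and six eligible integer values is compared with a post score that is not restricted. People admitted partly because of measurement error on the day will tend to move back towards the mean of the pool they came from, whatever the programme does. There is no comparison group to subtract this movement, and the planned model would report it as pre-post change.

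MoCA is the only pre-post measure of cognition, and the Abstract sets out "to evaluate cognitive, social, and mental well-being". If those screened average below the window centre, the shift is an apparent decline that could hide a benefit. If they average above it, the shift is an apparent gain. The other five constructs are not used for admission and carry no direct shift of this kind.

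The conflicting bounds are a separate matter. Staff cannot apply both rules to a person scoring 22 or 27 (26 with under 10 years of education).

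**Working it through.** **The plan's own figure.** 8 runs x 8 = 64 and 8 runs x 15 = 120, which reproduces the stated n = 64-120. The protocol gives no power, effect size or SD, so there is no power figure to reproduce.

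**Inputs.** From the protocol: the four windows above, with centres at 24.0 (22-26, 23-25) or 24.5 (22-27, 23-26). Assumed: screened mean m of 20 to 26, SD s of 3 to 4, retest correlation r of 0.7 to 0.9; 64 completers, or 96 (120 less an assumed 20% attrition). Scores are normal, rounded to integers 0-30. The screened pool is roughly symmetric, regression is linear, and there is no practice gain or natural change on retest.

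**Formulas, with no programme effect**

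- Expected change = (1 - r) x (m - mean of those selected).
- SD of change = sqrt[(1 - r)^2 x Var(selected pre score) + s^2 x (1 - r^2)].
- Rejection in the direction of the shift: noncentral t, two-sided 5%, independent participants. The nominal rate in one direction is 2.5%.

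**One case in full.** Window 22-27, m = 20, s = 4, r = 0.8. The selected mean is 23.77 and the selected variance 2.41.

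- Shift: 0.2 x (20 - 23.77) = -0.75.
- SD of change: sqrt(0.04 x 2.41 + 16 x 0.36) = 2.42.
- Noncentrality at 64 completers: 0.754 / 2.42 x 8 = 2.49, giving a 69% chance of a false significant decline.

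**Range over the four windows, s = 4, r = 0.8**

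| Screened mean | Shift (points) | False result in that direction, 64 / 96 completers | Screening yield (screened to enrol 120) |
|---|---|---|---|
| 20 | -0.71 to -0.83 | 64-78% / 81-92% | 18-32% (371-661) |
| 22 | -0.35 to -0.46 | 21-33% / 29-46% | 26-47% (258-462) |
| 23 to 25 | at most 0.28 either way | at most 15% / 20% | at mean 24: 29-54% (221-410) |
| 26 | +0.25 to +0.38 | 13-24% / 17-34% (false gain) | 26-52% (233-462) |

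**Extremes.** Over m = 20-26, s = 3-4 and r = 0.7-0.9 the shift runs from -1.25 (m = 20, s = 4, r = 0.7, window 23-26) to +0.58 (m = 26, s = 4, r = 0.7, window 23-25).

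**Sensitivity**

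- Higher r: at m = 20 and r = 0.9, the false-decline rate for windows 22-26 / 22-27 is 36% / 40% with 64 completers and 50% / 55% with 96.
- Mixed pools: if half of those enrolled come from a pool with mean 20 and half from one with mean 26, the shifts partly cancel. For window 22-26, (-0.71 + 0.35) / 2 = -0.18; over the four windows the result is -0.18 to -0.28.
- Practice gain: an assumed +0.5 points at m = 20, window 22-27, gives -0.75 + 0.50 = -0.25, and the false-decline rate at 64 completers falls from 69% to 13%. At m = 26 the same gain adds to the shift: +0.25 + 0.50 = +0.75.

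**Does adjustment help?** A random-intercept mixed model was simulated with a baseline covariate correlated 0.5 with true score (window 22-26, s = 4, r = 0.8, 120 enrolled, 20% random loss, no programme effect). The mean time effect was -0.74 at m = 20, -0.02 at 24 and +0.36 at 26. The shift remains.

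**The case against.** **The screened pool may sit near the window.** Partners are chosen partly for "ability to recruit potential participants with mild cognitive impairment into the programme", centres judge eligibility before referral, and known moderate or severe dementia is excluded. This stands, and it makes a small shift plausible. It does not settle the matter: recruitment sites include dementia day care as well as Active Ageing Centres, and nothing in the protocol fixes or reports the screened mean.

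**The formula needs a stable mean on retest.** This also stands. Screener and post test lie roughly 7 to 12 weeks apart (up to about 4 weeks before, 6 weeks of programme, 1 to 2 weeks after), so practice gain or natural change can offset or add to the shift. The error rates further assume independent participants from one pool, whereas runs are filled by centre.

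**The weight is limited.** "The exploratory study adopts a quasi-experimental and mixed-methods design", MoCA is one of six constructs, and a sensitivity table is detail that a statistical analysis plan may hold. That limits the importance. But the protocol itself fixes both the screener as pre value and the pre-post model.

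**The remedy relabels rather than repairs.** True. In simulation, a fresh MoCA taken after eligibility and before the programme gave a null change of about zero. It would add a test for every participant, which is hard to justify for one construct in an exploratory study.

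**A stronger reading.** A reader might infer that the MoCA result will be biased downwards, or that a false decline is more likely than not. The documents do not support this. The 64-92% rates need a screened mean of 20, two points below the lowest eligible score, and the full range includes zero and gains.

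**Conclusion.** The point holds as a possible bias of unknown sign in one outcome. That the same score selects and serves as baseline, without a comparator, follows from the text. The size does not: -1.25 to +0.58 points rests on assumed screened mean, SD and retest correlation, a roughly symmetric pool, linear regression and no change on retest. The practical difficulty is that a reader of the results could not tell which part of that range applies. The text should be changed, but the design of the study is not undermined.

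The conflict between the bounds needs no assumption. It neither depends on the regression argument nor adds weight to it, since the argument holds under either set of bounds.

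**What to change.** 1. In Component (i), where the constructs and the mixed models are described, state that the screener-to-post MoCA change is descriptive and is not by itself interpreted as a programme effect. Report it with a short sensitivity table over stated ranges of retest correlation (for example 0.7-0.9), screened mean (for example 20-26) and retest gain. Alternatively, report it with the aggregate mean and SD of all screened scores, if ethics approval allows.

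2. Separately, reconcile the MoCA bounds in the mental-capacity screening text and the Consent Process with those in the Inclusion and Exclusion Criteria, so that scores of 22 and 27 (26 with under 10 years of education) have one eligibility status throughout. Which bounds are intended is for the study team to settle.

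**Cost.** Wording, one table and a text correction; no new visit, test or data if assumed ranges are used. Using actual screened scores may need ethics clarification, because people who fail the screener never reach consent and the only consent waiver sought covers programme volunteers. The downside is that the only cognitive result becomes less conclusive, and with assumed inputs the sensitivity range is wide.
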